8.3 Reporting of Serious Adverse Events and Unanticipated Problems

When an adverse event has been identified, the study team will take appropriated action necessary to protect the study participant and then complete the Study Adverse Event Worksheet and log. The sponsor-investigator will evaluate the event and determine the necessary follow-up and reporting required.

8.3.1 Sponsor-Investigator reporting: notifying the Mayo IRB

The sponsor-investigator will report to the Mayo IRB any UPIRTSOs and Non-UPIRTSOs according to the Mayo IRB Policy and Procedures.

Any serious adverse event (SAE) which the Principal Investigator has determined to be a UPIRTSO will be reported to the Mayo IRB as soon as possible but no later than 5 working days after the investigator first learns of the problem/event.

The following information will be collected on the adverse event worksheet (and entered in the research database):

- Study ID
- Disease
- The date the adverse event occurred
- Description of the adverse event
- Relationship of the adverse event to the research (drug, procedure, or intervention*)
- Determination if the adverse event was expected
- The severity of the adverse event (severity scale described below**)
- If any intervention was necessary
- Resolution (was the incident resolved spontaneously, or after discontinuing treatment)
- Date of Resolution

The sponsor-investigator will review all adverse event reports to determine if specific reports need to be made to the IRB and FDA. The sponsor-investigator will sign and date the adverse event report when it is reviewed. For this protocol, only directly related SAEs/UPIRTSOs will be reported to the IRB.

* Relationship Index

The relationship of an AE to the Investigational Drug is a clinical decision by the sponsorinvestigator (PI) based on all available information at the time of the completion of the eCRF and is graded as follows:

1. Not related: a reaction for which sufficient information exists to indicate that the etiology is unrelated to the study drug; the subject did not receive the study medication or the temporal sequence of the AE onset relative to administration of the study medication is not reasonable or the event is clearly related to other factors such as the subject's clinical state, therapeutic intervention or concomitant therapy.

2. Unlikely: a clinical event, including laboratory test abnormality, with a temporal relationship to drug administration which makes a causal relationship improbable and in which other drugs, chemicals, or underlying disease provide plausible explanations.

3. Possible: a clinical event, including laboratory test abnormality, with a reasonable time sequence to administration of the drug but which could also be explained by concurrent disease or other drugs or chemicals; information on drug withdrawals may be lacking are unclear.

4. Probable: a clinical event including laboratory test abnormality, with a reasonable time sequence to administration of the drug, unlikely to be attributed to concurrent disease or other drugs or chemicals and which follows a clinically reasonable response on withdrawal (de-challenge): re-challenge information is not required to fulfil this definition.

5. Definite: a reaction that follows a reasonable temporal sequence from administration of the drug, or in which the drug level has been established in body fluids or tissues, that follows a known or expected response pattern to the suspected drug, and that is confirmed by improvement on stopping or reducing the dosage of the drug, and reappearance of the reaction on repeated exposure (re-challenge).

****** Severity Scale

The maximum intensity of an AE during a day should be graded according to the definitions below and recorded in details as indicated on the CRF. If the intensity of an AE changes over a number of days, then separate entries should be made having distinct onset dates.

1. Mild: AEs are usually transient, requiring no special treatment, and do not interfere with patient's daily activities.

2. Moderate: AEs typically introduce a low level of inconvenience or concern to the patient and may interfere with daily activities, but are usually ameliorated by simple therapeutic measures.

3. Severe: AEs interrupt a patient's usual daily activity and traditionally require systemic drug therapy or other treatment.

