1.3 Clinical Data to Date

A comprehensive search of the terms "hydroxocobalamin," "vitamin B12," "Cyanokit," "vasoplegia," "vasoplegic syndrome," and "liver transplantation" within MEDLINE and Embase was performed. Only 3 case reports with a total of 4 individual patients receiving B12 for the treatment of VS during LT surgeries were yielded from the MEDLINE search from 1946 to 2018 and Embase from 1988 to 2018. Although all 4 patients were reported to have favorable responses after B12 administration consistent with improved hemodynamics and reduced vasopressor requirements, no statistically significant conclusion could be drawn from the limited number of case reports.

A retrospective chart review was conducted for LT surgeries performed at our institution between January 2016 and June 2018. For patients with post-reperfusion VS treated with vasopressors, MB, and B12, hemodynamics variables and vasopressor requirements were reviewed. Fourteen of 401 LT patients during the study period presented with intraoperative VS and received vasopressors and MB as the first-line VS treatment due to the institutional protocol. Nine out of 14 patients receiving MB had an ineffective response defined as failure to improve hemodynamics or to reduce pressor requirements and were subsequently administered B12. Favorable changes in hemodynamic parameters with minimal averaged change of vasopressor requirements were observed after B12 administration. No major side-effect, medication associated complication, and post-operative mortality within 6 months of LT was observed. The institutional protocol required the usage of MB before B12 for VS treatment, causing the retrospective chart review to have clear comparison on the effectiveness of the 2 medications.

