- The risks of hydroxocobalamin: Common side effects include increased blood pressure, erythema, rash, nausea, decreased lymphocyte count, headache, and abnormal red urine color.

2 Study Objectives

Primary Objective

To assess the efficacy of hydroxocobalamin as compared to methylene blue on improving hemodynamic stability as measured by SVR, systemic blood pressure, and amount of vasopressors administered.

Secondary Objective

The secondary end point will examine the patient outcomes in the postoperative period as measured by early tracheal extubation after surgery, length of hospital and intensive care unit stay, perioperative complications (stroke, myocardial infarction, and acute renal failure), graft function, and survival rate.

3 Study Design

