3.1 General Description

This randomized, prospective, open label, pilot study will involve 20 LT patients with intraoperative vasoplegic syndrome. If vasoplegic syndrome is identified via SVR lower than 500 dynes-sec/cm⁻⁵, the patients will be randomized to receiving either IV methylene blue or hydroxocobalamin (10 patients in each group). The administration of assigned medication will only take place once during surgery if patient is exhibiting vasoplegia after the reperfusion of the new organ as demonstrated by SVR lower than 500 dynes-sec/cm⁻⁵ sustained for a period of more than 5 minutes despite the administration of vasopressors. The primary end point will examine the efficacy of the two medications on treating intraoperative vasoplegic syndrome. The SVR, blood pressure, and amount of administrations will be recorded.

[figure not shown]
If the patients still present with vasoplegic syndrome 30 minutes after receiving IV methylene blue or hydroxocobalamin during LT surgery, the vasoplegia treatment which the patients have not received in the operating room would be utilized as life-saving measures per standard of care practice. The patients will be excluded from the comparison study, but the data of frequency of failure to effectively treat vasoplegia via certain medication may be utilized in understanding the rate of failure to provide effective treatment.

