7.3 Subject Population(s) for Analysis

Each participant who received the study drug will be included in the primary analysis regardless of study withdrawal for any reason. In the event of any study withdrawals, in secondary analysis we will examine the sensitivity of our results to the exclusion of patients who withdrew.

8 Safety and Adverse Events

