For this study, the study treatment follow-up period is defined as 90 minutes following the last administration of study treatment.

Preexisting Condition

A preexisting condition is one that is present at the start of the study. A preexisting condition should be recorded as an adverse event if the frequency, intensity, or the character of the condition worsens during the study period.

General Physical Examination Findings

At screening, any clinically significant abnormality should be recorded as a preexisting condition. At the end of the study, any new clinically significant findings/abnormalities that meet the definition of an adverse event must also be recorded and documented as an adverse event.

Post-study Adverse Event

All unresolved adverse events should be followed by the sponsor-investigator until the events are resolved, the subject is lost to follow-up, or the adverse event is otherwise explained. At the last scheduled visit, the sponsor-investigator should instruct each subject to report, to the sponsor-investigator, any subsequent event(s) that the subject, or the subject's personal physician, believes might reasonably be related to participation in this study.

Hospitalization, Prolonged Hospitalization or Surgery

Any adverse event that results in hospitalization or prolonged hospitalization should be documented and reported as a serious adverse event unless specifically instructed otherwise in this protocol. Any condition responsible for surgery should be documented as an adverse event if the condition meets the criteria for an adverse event.

Neither the condition, hospitalization, prolonged hospitalization, nor surgery are reported as an adverse event in the following circumstances:

• Hospitalization or prolonged hospitalization for therapy of the target disease of the study, unless it is a worsening or increase in frequency of hospital admissions as judged by the clinical investigator.

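### In patients who receive both study drugs, the adverse event worksheet cannot place an event before or after the second drug, and the plan conflicts on how their postoperative outcomes are handled

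*Combined protocol and SAP*

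**What the plan says.** **Switching.** Section 3.1 sets the condition, "If the patients still present with vasoplegic syndrome 30 minutes after receiving IV methylene blue or hydroxocobalamin during LT surgery", and the consequence: "the vasoplegia treatment which the patients have not received in the operating room would be utilized as life-saving measures per standard of care practice". The next sentence reads "The patients will be excluded from the comparison study", although the frequency of failure may still be used.

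**Adverse events.** The Section 8.3.1 worksheet lists ten items. The only onset item is "The date the adverse event occurred". Relationship is to the research (drug, procedure or intervention), and the index grades it against one unnamed investigational drug. The severity scale also works by day. Section 8.1 says "the study treatment follow-up period is defined as 90 minutes following the last administration of study treatment". It does not say whether the second drug counts as study treatment.

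**Postoperative outcomes.** Section 2 states: "The secondary end point will examine the patient outcomes in the postoperative period as measured by early tracheal extubation after surgery", followed by length of stay, complications, graft function and survival. Section 7.3 says "Each participant who received the study drug will be included in the primary analysis regardless of study withdrawal for any reason". Section 4.4.1 lists treatment failure (the condition required another form of treatment) among reasons for discontinuing, and says that no data are collected on withdrawn subjects.

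**Prior experience.** Section 1.3 reports from the site's own chart review: "Nine out of 14 patients receiving MB had an ineffective response defined as failure to improve hemodynamics or to reduce pressor requirements"; these patients then received hydroxocobalamin.

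**The concern.** A switched patient has both agents on board within one operation. Section 1.5 lists raised blood pressure, nausea, headache and abnormal urine colour for both, so the type of event will not always identify the drug. Timing is then the main evidence, and the form does not collect it. An event 20 minutes after the first drug and one that follows the second drug carry the same date and are graded against the same unnamed drug.

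This matters because grading drives reporting. Section 8.2 requires immediate reporting of serious events that fall in the reporting period and are at least possibly related. Section 8.3.1 limits IRB reports to directly related ones. Both depend on which drug is meant and when the period starts.

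Postoperative outcomes come after any switch. What a between-arm summary of them means depends on whether switched patients are in it, and the plan gives incompatible answers.

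**Working it through.** The plan states no figure for how many patients will receive both drugs, so there is none to reproduce. The size can be gauged from its own data.

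**Inputs.** Methylene blue failures: 9 of 14 (Section 1.3). Arm size: 10 (Section 3.1). Switch point: 30 minutes (Section 3.1). Adverse event period: 90 minutes (Section 8.1). A failure rate for first-line hydroxocobalamin is not given.

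**1. Failure rate.** 9/14 = 0.643. Exact (Clopper-Pearson) 95% limits are the 0.025 quantile of Beta(9, 6) = 0.351 and the 0.975 quantile of Beta(10, 5) = 0.872.

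**2. Methylene blue patients expected to receive both drugs.** Expected number = 10p, and P(X ≥ 5) for X ~ Binomial(10, p):

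| p | Expected with both drugs | Expected with one drug | P(at least 1) | P(at least 5) |
|---|---|---|---|---|
| 0.351 | 3.5 | 6.5 | 0.987 | 0.25 |
| 0.643 | 6.4 | 3.6 | >0.999 | 0.90 |
| 0.872 | 8.7 | 1.3 | >0.999 | >0.999 |

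**3. Both arms together.** With methylene blue at 0.643 and hydroxocobalamin failure *assumed* at 20%, 40% or 64%, the expected number with both drugs is 6.4 + 2.0 = 8.4, 6.4 + 4.0 = 10.4, or 6.4 + 6.4 = 12.9 (unrounded) of 20.

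**4. The 90-minute period.** There are two readings of Section 8.1:
- The second drug is not study treatment, so the period runs from the first drug. With a switch at 30 minutes, (90 − 30)/90 = 67% of it falls after the second drug. With a switch at 45 minutes (an assumption), the share is (90 − 45)/90 = 50%.
- The second drug is study treatment, so the period restarts and ends at least 30 + 90 = 120 minutes after the first drug.

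Under either reading, a date cannot show whether an event fell inside the period.

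**5. Switched patients in the postoperative summaries.**

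| Section | Switched patients | Consequence |
|---|---|---|
| 3.1 | Excluded from the comparison | Selection on response: about 3.6 of 10 methylene blue patients remain (1.3 to 6.5) |
| 7.3 | Kept in the primary analysis if treated | Mixed exposure: about 6.4 of 10 methylene blue patients had both drugs |
| 4.4.1 | Meet a listed reason for withdrawal | No data collected if withdrawn |

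No version gives the effect of one drug alone in everyone randomised. Section 7.3 speaks of the primary analysis only, so the secondary outcomes have no explicit rule. Section 4.4.1 also sits badly with Section 8.2, which requires all adverse events during the study period to be recorded.

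**The case against.** The strongest reply is that this is a descriptive pilot of 20 patients. Section 3.6 names no primary safety endpoint, and Section 7 plans no adverse event comparison by arm. The causality index tells the investigator to use all available information, including temporal sequence, concomitant therapy and other drugs. Events go into the source document at once (Section 8.2), intraoperative events are in the health record (Section 3.7), and concomitant medications are collected at Visit 2 (Section 6.4). Clock times may therefore be recoverable. Nausea and headache are unlikely to be voiced during surgery, and the urine change listed for hydroxocobalamin is specifically red, so the overlap in side effects is smaller than the lists suggest.

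Much of this stands, and it rules out several stronger readings:
- A reader might infer that no adverse event or outcome can be attributed to the assigned drug. That does not follow, because patients given one drug are unaffected.
- A reader might infer that one drug's side effects will be counted against the other arm. No text assigns events to arms, and no between-arm safety comparison is planned.
- A reader might infer that the plan treats postoperative outcomes as drug effects. Section 2 says only that they will be examined; a drug-level reading is plausible beside a two-drug primary objective, but is not stated.
- A reader might take the time before the switch as one third of the reporting period. That holds only if the period runs from the first drug, whereas Section 8.1 counts from the last study treatment.

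What the reply does not remove is that every causality grade leans on timing that the worksheet does not request. For a switched patient, nothing says whether the second drug is the study drug or an other drug. That times may be recoverable makes the fix easy; it does not make it part of the plan.

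**Conclusion.** The point holds for patients who receive both study drugs, and only for them. Their adverse event record cannot order an event against the second drug, name the drug graded, or settle whether the event fell in the 90-minute period. Their postoperative outcomes are governed by sections that conflict.

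On the site's own data this could be about 6 of 10 methylene blue patients, with 3.5 to 8.7 over the confidence interval. The 0.90 probability of at least 5 treats 9/14 as known and falls to 0.25 at the lower limit, so a mostly two-drug methylene blue arm is likely but not established. The estimate assumes that failure as defined in the chart review (no improvement in haemodynamics or no reduction in pressors) resembles persistent vasoplegia at 30 minutes. The hydroxocobalamin rate is unknown.

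No sample size or error rate is affected. This should be corrected because the pilot exists to supply data for a larger study, and timing is best captured prospectively.

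**What to change.** **Adverse event worksheet (8.3.1).** Replace date with date and clock time of onset. Add the start time of each study drug received, and grade relationship to each drug separately.

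**Reporting period (8.1).** State whether the second drug counts as study treatment, and so whether the 90 minutes restart.

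**Presentation (7.2).** List adverse events by randomised arm, split into before and after the second drug.

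**Analysis population (3.1, 4.4.1, 7.3).** Reconcile the three so that switched patients' data are collected and summarised in their randomised arm. This replaces the exclusion in 3.1 and should be stated openly as a change of rule. Print the number who received both drugs beside each postoperative outcome, and describe that comparison as one of starting drug.

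**Cost.** A few CRF fields, which the anaesthesia record should be able to supply, one split listing, and edits to the sections above. The secondary claim becomes narrower: starting drug rather than drug. No change to treatment or to the switching rule is proposed.

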8.4 Medical Monitoring

It is the responsibility of the Principal Investigator to oversee the safety of the study at his/her site. This safety monitoring will include careful assessment and appropriate reporting of adverse events as noted above, as well as the construction and implementation of a site data and safety-monitoring plan (see section 10 "Study Monitoring, Auditing, and Inspecting"). Medical monitoring will include a regular assessment of the number and type of serious adverse events.

9 Data Handling and Record Keeping

9.1 Confidentiality

Information about study subjects will be kept confidential and managed according to the requirements of the Health Insurance Portability and Accountability Act of 1996 (HIPAA). Those regulations require a signed subject authorization informing the subject of the following:

- What protected health information (PHI) will be collected from subjects in this study
- Who will have access to that information and why
- Who will use or disclose that information
- The rights of a research subject to revoke their authorization for use of their PHI.

In the event that a subject revokes authorization to collect or use PHI, the investigator, by regulation, retains the ability to use all information collected prior to the revocation of subject authorization. For subjects that have revoked authorization to collect or use PHI, attempts should be made to obtain permission to collect at least vital status (long term survival status that the subject is alive) at the end of their scheduled study period.

9.2 Source Documents

Source data is all information, original records of clinical findings, observations, or other activities in a clinical trial necessary for the reconstruction and evaluation of the trial. Source data are contained in source documents. Examples of these original documents, and data records include: hospital records, clinical and office charts, laboratory notes, memoranda, pharmacy records, recorded data from automated instruments, x-rays, subject files, and records kept at the pharmacy, at the laboratories, and at medico-technical departments involved in the clinical trial.

9.3 Case Report Forms

All data necessary for this study will be obtained from EHR and recorded on the electronic Case Report Forms (CRFs) created in REDCap. All missing data will be explained.

Data Management

Study data to be collected and managed using EHR and transcribed into electronic CRFs in REDCap, electronic data capture software, hosted by CTSA at Mayo Clinic. REDCap (Research

Electronic Data Capture) is a secure, web-based application designed to support data capture for research studies, providing 1) an intuitive interface for validated data entry; 2) audit trails for tracking data manipulation and export procedures; 3) automated export procedures for seamless data downloads to common statistical packages; and 4) procedures for importing data from external sources.

Data Processing

All study date will be stored and analyzed at Mayo Clinic in Florida using the REDCap electronic data capture tool.

Data Security and Confidentiality

All source documents including clinical findings, observations or other activities will be stored in a REDCap database that will be designed by an Investigator. Access to the REDCap database will be limited to the Principal Investigator, Investigators, Study Team members, and Statistician.

Data Quality Assurance

Once the study is completed the Principal Investigator will randomly select 3 participants and compare the data documented in the EHR with what is entered into the REDCap database. If there is any discrepancy, the Principal Investigator and/or Investigators will cross-reference all 20 patients to ensure accuracy.

Data Clarification Process

For any data query the Principal Investigator and Investigators will meet to clarify the data queried and make corrections based on consensus.

9.4 **Records Retention**

The sponsor-investigator will maintain records and essential documents related to the conduct of the study. These will include subject case histories and regulatory documents.

The sponsor-investigator will retain the specified records and reports for;

- 1. Up to 2 years after the marketing application is approved for the drug; or, if a marketing application is not submitted or approved for the drug, until 2 years after shipment and delivery of the drug for investigational use is discontinued and the FDA has been so notified. OR
- 2. As outlined in the Mayo Clinic Research Policy Manual –"Retention of and Access to Research Data Policy"

10 Study Monitoring, Auditing, and Inspecting

